### 10. CHANGES FROM PROTOCOL-SPECIFIED ANALYSES

There are no major changes between the protocol-defined statistical analyses and those presented in this statistical plan.

### 12. DATA NOT COVERED BY THIS PLAN

Not Applicable.

### 13. APPENDIX A: GRADING LABORATORY VALUES ACCORDING TO CTCAE VERSION 5

	Grade 1	Grade 2	Grade 3	Grade 4
Hematology				
Eosinophils (Eosinophilia)	> ULN and > baseline		Steroids initiated	
Hemoglobin, increased	Increase in > 0 - 2 g/dL	Increase in > 2 - 4 g/dL	Increase in > 4 g/dL	
Hemoglobin, decreased (Anemia)	< LLN - 10.0 g/dL	< 10.0 – 8.0 g/dL	< 8.0 g/dL OR transfusion indicated	Life-threatening consequences or urgent intervention required
Leukocytes, increased (Leukocytosis)			> 100,000/mm 	Clinical manifestations of leucostasis or urgent intervention indicated
Leukocytes, decreased	< LLN – 3000/mm 	< 3000 – 2000/mm 	< 2000 – 1000/mm 	< 1000/mm 
Lymphocytes, increased		> 4000 – 20,000/mm 	> 20,000/mm 	
Lymphocytes, decreased	< LLN – 800/mm 	< 800 – 500/mm 	< 500 – 200/mm 	< 200/mm 
Neutrophils, decreased	< LLN – 1.5 x 10  /L	< 1.5 x – 1.0 x 10  /L	< 1.0 – 0.5 x 10  /L	< 0.5 x 10  /L
Platelet count, decreased	< LLN – 75.0 x 10  /L	< 75.0 x – 50.0 x 10  /L	< 50.0 x – 25.0 x 10  /L	< 25.0 x 10  /L
Serum Chemistry				
Albumin, low (Hypoalbuminemia)	< LLN – 30 g/L	< 30 – 20 g/L	< 20 g/L	Life-threatening consequences or urgent intervention required
Amylase, increased	> ULN – 1.5 x ULN	> 1.5 x – 2.0 x ULN OR > 2.0 x – 5.0 x ULN without symptoms	> 2.0 x – 5.0 x ULN with signs or symptoms OR > 5.0 x ULN without symptoms	> 5.0 x ULN with signs or symptoms
Alanine aminotransferase, increased	Normal baseline: > ULN – 3.0 x ULN Abnormal baseline: 1.5 x – 3.0 x baseline	Normal baseline: > 3.0 x – 5.0 x ULN Abnormal baseline: > 3.0 x – 5.0 x baseline	Normal baseline: > 5.0 x – 20.0 x ULN Abnormal baseline: > 5.0 x – 20.0 x baseline	Normal baseline: > 20.0 x ULN Abnormal baseline: > 20.0 x baseline
Alkaline Phosphatase, increased	Normal baseline: > ULN – 2.5 x ULN Abnormal baseline: 2.0 x – 2.5 x baseline	Normal baseline: > 2.5 x – 5.0 x ULN Abnormal baseline: > 2.5 x – 5.0 x baseline	Normal baseline: > 5.0 x – 20.0 x ULN Abnormal baseline: > 5.0 x – 20.0 x baseline	Normal baseline: > 20.0 x ULN Abnormal baseline: > 20.0 x baseline
Aspartate aminotransferase, increased	Normal baseline: > ULN – 3.0 x ULN Abnormal baseline: 1.5 x – 3.0 x baseline	Normal baseline: > 3.0 x – 5.0 x ULN Abnormal baseline: > 3.0 x – 5.0 x baseline	Normal baseline: > 5.0 x – 20.0 x ULN Abnormal baseline: > 5.0 x – 20.0 x baseline	Normal baseline: > 20.0 x ULN Abnormal baseline: > 20.0 x baseline
Bicarbonate, decreased	< LLN and no intervention initiated			

	Grade 1	Grade 2	Grade 3	Grade 4
Calcium (corrected), high (Hypercalcemia)	> ULN – 2.9 mmol/L	> 2.9 – 3.1 mmol/L or symptomatic	> 3.1 – 3.4 mmol/L or hospitalization indicated	> 3.4 mmol/L or life-threatening consequences
Calcium (corrected), low (Hypocalcemia)	< LLN – 2.0 mmol/L	< 2.0 – 1.75 mmol/L or symptomatic	< 1.75 – 1.5 mmol/L or hospitalization indicated	< 1.5 mmol/L or life-threatening consequences
Creatinine, increased	> ULN – 1.5 x ULN	Normal baseline: > 1.5 – 3.0 x ULN Abnormal baseline: > 1.5 x – 3.0 x baseline	> 3.0 – 6.0 x ULN OR > 3.0 x baseline	> 6.0 x ULN
Creatine phosphokinase, increased	> ULN – 2.5 x ULN	> 2.5 – 5.0 x ULN	> 5 – 10 x ULN	> 10 x ULN
Gamma glutamyl transferase, increased	Normal baseline: > ULN – 2.5 x ULN Abnormal baseline: 2.0 x – 2.5 x baseline	Normal baseline: > 2.5 x – 5.0 x ULN Abnormal baseline: > 2.5 x – 5.0 x baseline	Normal baseline: > 5.0 x – 20.0 x ULN Abnormal baseline: > 5.0 x – 20.0 x baseline	Normal baseline: > 20.0 x ULN Abnormal baseline: > 20.0 x baseline
Glucose, high (Hyperglycemia)	Abnormal glucose above baseline with no medical intervention	Change in daily management from baseline for a diabetic or oral antiglycemic agent initiated or workup for diabetes	Insulin therapy initiated or hospitalization indicated	Life-threatening consequences or urgent intervention indicated
Glucose, low (Hypoglycemia)	< LLN - 3.0 mmol/L	< 3.0 - 2.2 mmol/L	< 2.2 - 1.7 mmol/L	< 1.7 mmol/L or life-threatening consequences or seizures
Potassium, high (Hyperkalemia)	> ULN – 5.5 mmol/L	> 5.5 – 6.0 mmol/L or intervention indicated	> 6.0 – 7.0 mmol/L or hospitalization indicated	> 7.0 mmol/L or life-threatening consequences
Potassium, low (Hypokalemia)	< LLN – 3.0 mmol/L without symptoms	< LLN – 3.0 mmol/L with symptoms or intervention indicated	< 3.0 – 2.5 mmol/L or hospitalization indicated	< 2.5 mmol/L or life-threatening consequences
Sodium, high (Hypernatremia)	> ULN – 150 mmol/L	> 150 - 155 mmol/L or intervention initiated	> 155 – 160 mmol/L or hospitalization indicated	> 160 mmol/L or life-threatening consequences
Sodium, low (Hyponatremia)	< LLN – 130 mmol/L	125-129 mmol/L without symptoms OR 120-124 mmol/L regardless of symptoms	125-129 mmol/L with symptoms OR 120-124 mmol/L regardless of symptoms	< 120 mmol/L or life-threatening consequences
Total bilirubin, increased	Normal baseline: > ULN – 1.5 x ULN Abnormal baseline: > 1.0 x – 1.5 x baseline	Normal baseline: > 1.5 x – 3.0 x ULN Abnormal baseline: > 1.5 x – 3.0 x baseline	Normal baseline: > 3.0 x – 10.0 x ULN Abnormal baseline: > 3.0 x – 10.0 x baseline	Normal baseline: > 10.0 x ULN Abnormal baseline: > 10.0 x baseline
Coagulation				

	Grade 1	Grade 2	Grade 3	Grade 4
INR, increased	Not on anticoagulant: > 1.2 – 1.5 On anticoagulant: > 1.0 x – 1.5 x baseline OR monitoring indicated	Not on anticoagulant: > 1.5 – 2.5 On anticoagulant: > 1.5 x – 2.5 x baseline OR dose adjustment indicated	Not on anticoagulant: > 2.5 On anticoagulant: > 2.5 x baseline OR bleeding	
Activated Partial Thromboplastin Time, prolonged	> ULN – 1.5 x ULN	> 1.5 x – 2.5 x ULN	> 2.5 x ULN or bleeding	

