ECG ⁴	X	X		X	X	X	X	X	X	X	X	X
Vital Signs (BP, temp, pulse ox., RR, heart rate) perform before other evaluations	X	X		X	X	X	X	X	X	X	X	X
Clinical Labs (heme, coag, chem, UA, Urine electrolytes)	X	X		X (pre-dose)	X (pre-dose)	X (pre-dose)	X		X	X	X	X
PK ²				X	X	X	X	X				
Plasma metabolite ID				X	X	X	X		X	X		
Urine collection for excretion and metabolite ID ³						X	X					
Chest X-ray (PA and Lateral) ⁵	X									X	X	X
Spirometry ¹	X	X							X	X	X	X
Concomitant Meds/Therapies	X	X							X	X	X	X
Adverse Events	X	X							X	X	X	X
Dose Administration (PBO or Active)												
Urine Cotinine	X											
Anti-drug antibodies		X									X	

1. On dosing days (Days 1,2,3), completed at immediate pre-dose, 15 min (± 10 min), 60 min (± 10 min), 120 min (± 10 min). On non-dosing days, only completed once per visit.
2. Plasma PK collected:
 - a. Day 1: Pre-dose, then based on start of inhalation 30, 60, 120 min, 4, 6, 8, 16 hours.
 - b. Day 2: Pre-dose (Day 1, 24 hr timepoint), then based on start of inhalation, 1, 2, 4 hours
 - c. Day 3: Pre-dose (Day 2, 24 hr timepoint), then based on start of inhalation, 30, 60, 120 min, 4, 6, 8, 16, 24 (on Day 4), 48 hours (on Day 5).
3. Urine collected cumulatively from 0-6 hours and 6-24 hours post dose on Day 3 through Day 4. Subject should void pre-dose on Day 3. Metabolite ID will be performed on urine samples collected (pooled analysis).
4. On dosing days, ECG performed pre-dose (-4hrs) and 2 hours (± 10 min) post-dose; any abnormal ECG's will be repeated in triplicate with each measurement approximately 1 minute apart.
5. Chest x-ray to be performed at screening, day 15, and day 29 (or early termination). At all other times, any AE consistent with lower respiratory infection, dyspnea, or bronchospasm will trigger a chest X-ray and PFT measurement.

Note: R = randomize.

Table 1.2: Cohort 5:

Assessment	Screen	Day 0 Confine	R	Day 1	Day 2	Day 3	Day 4	Day 5	Day 8	Day 18	Day 19	Day 29 EOS	Early Term.
Visit Windows	Days -28 to -1			± 5 min for 30 min post dose PK draw and ± 10 min for all other post dose PK timepoints only					± 2 d	± 3 d	+ 2d	± 2 d	
Informed Consent	X												
Eligibility Criteria	X												
Body Mass Index/Weight/Height	X			X					X	X		X	X
Demographics	X												
Medical History	X												
Drug Screen	X												
Hepatitis/HIV Serology Screen	X												
Physical Exam (may be symptom directed after Day 1)	X	X		X (pre-dose)	X	X	X	X	X	X		X	X
FSH (in women of post-menopausal age only)	X												

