## 5. DEFINITIONS

### Study Day:

Day of study relative to the date of first dose of active drug or placebo. First dose date will be considered as Day 1. Calculated prior to first dose date as (date of measurement – date of first dose) and calculated after first dose date as (date of measurement – date of first dose + 1).

Baseline:

The last observation prior to the first dose of active drug or placebo. The baseline value may be an unscheduled or repeated measurement.

Change (absolute) from baseline:

The arithmetic difference between a post-baseline value and baseline for a given time point: change (absolute) from baseline = (post-dose value – baseline value).

Percent change from baseline:

The percent change between a post-baseline value and baseline for a given time point: [(post-dose value – baseline value) / baseline value] \*100%

Treatment-emergent AEs (TEAEs):

TEAE will be derived as any AEs occurring on or after the first dose.

Treatment-emergent SAEs (TESAEs):

TESAE will be derived as any serious AEs occurring on or after the first dose.

Concomitant Medications:

Concomitant medications will be derived as any medications with an end date on or after the first dose.

Use of medications at baseline:

For each of the following medications: CFTR modulators, inhaled hypertonic saline, inhaled bronchodilators, chronic inhaled antibiotics, inhaled corticosteroids, dornase alfa, and azithromycin, any use within 30 days prior to first dose will be considered as use at baseline. Dornase alfa and azithromycin will be identified by the Preferred Drug Name as coded by WHODrug. All other medications will be identified as recorded on the CF-Concomitant Medications eCRF.

Sputum pseudomonas status at baseline:

Any pseudomonas (as collected on the Airway Infection eCRF) present within 30 days prior to first dose will be considered as positive at baseline.

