### **9.5.2      Laboratory Test Results**

Laboratory assessments include clinical chemistry, coagulation, hematology, urinalysis, and urine electrolytes. Microscopic urinalysis will also be performed as needed, with results listed by subject but not otherwise summarized. Clinical laboratory values will be expressed using the International System of Units (SI).

Descriptive statistics summaries of quantitative laboratory tests will be provided by scheduled visit. Derived changes and percent changes from baseline to each scheduled postdose visit will be included. Additionally, descriptive statistics for the peak post-baseline values will be included for the chemistry lab tests: ALT, AST, ALP, and BILI, and descriptive statistics for the lowest post-baseline values and lowest overall values will be provided for the hematology lab tests: HGB and PLT. Laboratory test values above or below the limits of detection will be set to the upper or lower limit values, respectively, for inclusion in the descriptive statistics summaries; values will be reported without imputation in the listings.

Plots of mean (+/- SD) key laboratory test results over time will be provided by study day. The key laboratory tests to be included will be: alanine aminotransferase, aspartate aminotransferase, total bilirubin, creatine kinase, creatinine, potassium, and sodium. SD bars below 0 will be set to 0.

Scatter plots of peak post-baseline total bilirubin [divided by upper limit of normal (ULN)] vs peak post-baseline alanine aminotransferase [divided by ULN] will be provided to visually evaluate drug-induced serious hepatotoxicity.

---

Additionally, select laboratory tests from serum chemistry, coagulation, and hematology will be programmatically graded using the National Cancer Institute (NCI) Common Terminology Criteria for Adverse Events (CTCAE) version 5.0 grading criteria (Appendix A). Laboratory test values above or below the limits of detection will be set to the upper or lower limit values, respectively, for programmatic grading. Using the CTCAE grades, shift tables describing changes from baseline to the maximum post-baseline grade will be provided for clinical chemistry, coagulation, and hematology laboratory results. The number and percent of subjects will be reported in each shift category. Assessments which are missing a baseline value or which are not graded at baseline will be summarized as unknown.

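### Grade 1 for increased haemoglobin has no upper-limit condition, minimum rise or named reference value, so the Grade 1 cell of its shift table is largely chance

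*SAP*

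**What the plan says.** SAP Section 9.5.2 states that "select laboratory tests from serum chemistry, coagulation, and hematology will be programmatically graded" using CTCAE version 5.0 as set out in Appendix A (Section 13). It then says that "shift tables describing changes from baseline to the maximum post-baseline grade will be provided".

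In Appendix A, the row for increased haemoglobin gives Grade 1 as "Increase in > 0 - 2 g/dL" and Grade 2 as "Increase in > 2 - 4 g/dL"; Grade 3 is a rise above 4 g/dL. No cell in the row mentions the ULN or says what the rise is measured from. In the same table, Grade 1 eosinophilia requires "> ULN and > baseline".

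SAP Section 5 defines baseline as a single value: "The last observation prior to the first dose of active drug or placebo". On the baseline side of the shift, Section 9.5.2 adds: "Assessments which are missing a baseline value or which are not graded at baseline will be summarized as unknown".

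**The concern.** The natural reading is that the rise is measured from baseline. A post-dose value 0.1 g/dL above one pre-dose reading, well inside the normal range, is then Grade 1. Because a program does the grading, no clinical judgement screens such values out. Because the table keeps the worst grade over all visits, one such value is enough.

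The Data Analysis part of the protocol synopsis gives shift tables the job of describing the incidence of laboratory abnormalities. A small rise within normal limits is not an abnormality, yet this row would count it as one in most subjects on active drug and on placebo alike. A reader of the study report could take a high Grade 1 percentage as a finding, or could miss a real mild effect hidden in it.

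The row is unusual in its table. Most rows for high values start at the ULN. Leukocytes, lymphocytes and INR off anticoagulants use fixed cut-offs, and high glucose requires an abnormal value. Bilirubin and INR do have cells that start at any rise above baseline, but only for subjects with an abnormal baseline or on anticoagulants. Increased haemoglobin is the only such row that applies a bare rise to every subject.

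The baseline side has its own gap. A rise from baseline is zero at baseline by construction, so the row may count as ungraded there. The table could then show most subjects moving from unknown to Grade 1.

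**Working it through.** The plan states no expected flag rate, so there is no figure of its own to reproduce.

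**Inputs from the documents.** Scheduled draws after the Day 1 pre-dose baseline, from the clinical laboratory rows of the protocol's schedules of assessments:
- Cohorts 1–4 (Table 1.1): Days 2, 3, 4, 8, 15, 29, so k = 6.
- Cohort 5 (Table 1.2): Days 2, 3, 4, 8, 18, 29, so k = 6.
- Cohort 6 (Table 1.4): Days 2, 8, 15, 22, 29, 30, 36, 43, 57, 71, 85, 113, so k = 12.
- Cohorts 2b–4b (Table 1.3): the marks in this row cannot be read in the text available. There are 12 visits after Day 1, so k is at most 12.

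**Inputs assumed, because the documents do not give them.** Within-subject SD of haemoglobin 0.3–0.6 g/dL; values reported to 0.1 g/dL; mean post-baseline drift from −0.5 to +0.3 g/dL.

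**Step 1: no drift and no ties.** With no drug effect, the baseline value and the k later values are exchangeable. Each of the k + 1 values is equally likely to be the largest, so baseline is the largest with probability 1/(k + 1). Hence

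P(at least one later value exceeds baseline) = 1 − 1/(k + 1) = k/(k + 1), whatever the SD.

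- k = 6: 6/7 = 85.7%. For 36 healthy volunteers, 36 × 6/7 = 30.9 expected at Grade 1 or above.
- k = 12: 12/13 = 92.3%. For 24 patients in Cohort 6, 24 × 12/13 = 22.2 expected.

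**Step 2: relaxing the assumptions.** Simulation with 100,000 subjects per case, over the SD range above. All rows use values rounded to 0.1 g/dL; a tie is not a rise.

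| Setting | k = 6 | k = 12 (Cohort 6) |
|---|---|---|
| Rounding only | 82–84% | 90–91% |
| Rounding and serial correlation | 82–85% | 90–91% |
| Mean drift −0.3 g/dL | 53–72% | 65–82% |
| Mean drift −0.5 g/dL | 31–61% | 43–73% |
| Mean drift +0.3 g/dL | 92–96% | 96–98% |

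**Step 3: higher grades.** With rounding and no drift, the chance of a maximum rise above 2 g/dL (Grade 2 or higher) is 0–4% for k = 6 and 0–6% for k = 12.

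**Step 4: effect of a ULN condition.** For illustration, assume a between-subject SD of 1.0 g/dL and a ULN 2.0–2.5 g/dL above the population mean. The chance that the largest later value exceeds both ULN and baseline is about 1–10% for k = 6 and 2–15% for k = 12. These are upper bounds on the Grade 1 rate under the fix, since they count every subject who exceeds both limits.

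**The case against.** **The rate is conditional.** The 86% and 92% need no drift, no ties and complete visits. A fall in haemoglobin is plausible: Table 1.1 schedules 22 pharmacokinetic samples over Days 1–5 (8 + 4 + 10) on top of the clinical laboratory draws. This stands, and the range under drift has to be quoted with the figures. Even so, the lowest case tested flags about 3 in 10 subjects although mean haemoglobin is falling.

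**Only Grade 1 is affected.** A reader might infer that the whole haemoglobin-increase table cannot separate drug from noise. It can above 2 g/dL, where chance alone flags few subjects.

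**Differing draw counts.** A reader might also infer that 6 draws against 12 biases comparisons between cohorts. The documents do not show this. SAP Section 9 summarises healthy volunteers and CF patients separately, all healthy-volunteer cohorts have 6 draws, and the count for Cohorts 2b–4b cannot be read but is at most the 12 of Cohort 6. No imbalance within a table is demonstrated.

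**The row may follow its declared source.** Whether it reproduces the cited grading criteria cannot be checked from the documents, so no transcription error is alleged. A faithful copy would still be uninformative when a program applies it to every value.

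**The information exists elsewhere.** SAP Section 9.5.2 also gives haemoglobin values and changes by visit, and a listing of out-of-range values with reference ranges. Protocol Section 11.2 makes a laboratory abnormality an adverse event only if it is clinically significant or has clinical sequelae, so a programmed Grade 1 does not feed the primary endpoint. SAP Section 2.2 plans no formal testing. All of this stands and limits the importance of the point.

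**A ULN condition on every band would go too far.** A real rise of more than 2 g/dL within the normal range would become ungraded. This also stands, and the fix is confined to Grade 1.

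**Conclusion.** The point holds for the Grade 1 cell of one descriptive safety table. If the rise is measured from baseline, applying the rule as written would label most subjects Grade 1 by chance: 86% with 6 draws and 92% with 12, given exchangeable values, no ties and all scheduled draws done. Under an assumed mean fall of 0.3–0.5 g/dL the range is about 31–72% and 43–82%; under an assumed rise of 0.3 g/dL it is higher than the no-drift figures. Missed visits would lower these rates and unscheduled draws would raise them.

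Active and placebo are inflated alike, so the cell carries almost no information about the drug. Grades 2 and 3 remain usable, with a chance rate of about 0–6% under no drift. The primary endpoint and the sample size are untouched. This is a cheap improvement, not a flaw that threatens the trial's conclusions.

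**What to change.** Amend the increased-haemoglobin row of SAP Appendix A and its handling in Section 9.5.2:

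1. State that the rise is measured from the baseline defined in Section 5.
2. Assign Grade 1 only when the post-baseline value is above both the ULN and baseline, as the eosinophil row does.
3. Keep Grade 2 (above 2 to 4 g/dL) and Grade 3 (above 4 g/dL) as rises from baseline, without a ULN condition.
4. Show the baseline category for this row as Grade 0 when a baseline value exists, and keep unknown for a missing baseline.

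The cost is one table row and a line of programming specification. The downside is small: if the row reproduces the cited criteria, the SAP needs one sentence recording the departure. Rises of up to 2 g/dL that stay within the normal range would no longer be graded, but they remain visible in the by-visit change summaries.

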Blood samples will be collected from each subject for metabolic analysis per the SOA. Samples will be frozen at -80°C for analysis outside of this study.

Urine collections will be performed after dosing per the SOA.

Data Analysis:

Healthy volunteers and CF patients will be analyzed separately.

For each healthy volunteers and CF population, subjects will be analyzed by cohorts. Placebo subjects from each cohort will be pooled. In addition, CF patients will also be analyzed in aggregate and separately based on CFTR mutation status and based on use or no use at baseline of a stable regimen (last 2 months) of CFTR modulators/correctors as well as use or no use at baseline of inhaled hypertonic saline.

Screening, Compliance, Tolerability and Safety Data:

In general, safety analyses will be performed based on Safety Analysis Set, which includes all enrolled subjects who receive at least one dose of study drug (placebo or active). Post-dose safety assessments will be compared with measurements recorded at baseline. Treatment-emergent AEs will be summarized using the Medical Dictionary for Regulatory Activities (MedDRA) under version 23.0 or later by System Organ Class (SOC) and Preferred Term (PT). The incidence and frequency of treatment-emergent AEs, SAEs, related AEs, related SAEs, and AEs leading to discontinuation, will be summarized by cohort per SOC, PT, and severity. All AEs, SAEs will also be presented in listings. The duration of AEs will be determined and included in listings, along with the action taken and outcome. The incidence of laboratory abnormalities will be assessed using descriptive summary statistics and shift tables. Vital sign measurements will be summarized at each scheduled time point using descriptive statistics. Abnormal physical examination findings will be summarized by time point and presented in subject listings. ECG parameters, changes from baseline, and qualitative assessments will be summarized. Pregnancy and FSH test results will be listed separately.

Pharmacokinetics:

Plasma concentrations of ARO-ENaC product constituents will be used to calculate the following PK parameters:

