All laboratory data will be listed by subject. A separate listing of abnormal and out-of-range laboratory values will also be provided. Both listings will include normal reference ranges and flags (low, high, abnormal).

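### The only laboratory shift tables rest on CTCAE grades that leave most total leukocyte rises ungraded, cannot rank high glucose and omit several collected tests, so no table counts by dose group who left the reference range on these tests

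*SAP*

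**What the plan says.** The protocol synopsis, under its safety data analysis, states: "The incidence of laboratory abnormalities will be assessed using descriptive summary statistics and shift tables". Protocol Section 12.3 also says that the incidence of laboratory abnormalities will be summarized. It does not mention shift tables, and it adds that variables without a code will be listed as below, within or above the laboratory's normal limits.

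SAP Section 9.5.2 says that selected chemistry, coagulation and hematology tests will be graded by program with CTCAE version 5.0, using Appendix A. It continues: "Using the CTCAE grades, shift tables describing changes from baseline to the maximum post-baseline grade will be provided". No other laboratory shift table is described. Values that are missing or not graded at baseline are shown as unknown.

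Appendix A (SAP Section 13) contains these entries:

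- **Total leukocytes, increased:** in the row "Leukocytes, increased (Leukocytosis", Grades 1 and 2 are empty, Grade 3 is above 100,000/mm3, and Grade 4 is "Clinical manifestations of leucostasis or urgent intervention indicated".
- **Neutrophils:** a row for decreases only.
- **Glucose, high:** Grade 1 is "Abnormal glucose above baseline with no medical intervention". Grades 2 to 4 are defined by treatment started or changed, diagnostic workup, hospitalization or clinical consequences.

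The other laboratory outputs in Section 9.5.2 are by-visit descriptive statistics with changes from baseline, plots of seven key tests, peak or lowest values for a few tests, and by-subject listings. Of the listings it says: "Both listings will include normal reference ranges and flags (low, high, abnormal".

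**The concern.** In a first-in-human study whose primary endpoint is adverse events, a basic laboratory safety question is how many subjects in each dose group were normal at baseline and abnormal afterwards. A shift table answers it directly. Here the shift table can answer it only where Appendix A has a cut that a program can apply to a laboratory value.

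For total leukocytes that cut lies far above the range in which an ordinary rise would fall. For raised neutrophils, and for the chemistry tests without a row, there is no cut. For high glucose a small rise and a very large one get the same grade. A reader of the study report could take an empty leukocyte-increase row, or a glucose row that stops at Grade 1, as evidence that nothing happened or that what happened was mild. Neither conclusion would follow from the table.

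**Working it through.** No plan figure is to be reproduced. The check compares the Appendix A rows with the collected panel and with the other planned outputs.

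**1. Total leukocytes, increased.** The only numeric cell is Grade 3. Since 1 mm3 is 10^-6 L, 100,000/mm3 = 100,000 × 10^6 per L = 100 × 10^9/L. The documents give no upper limit of normal (ULN). Assuming 10 to 11 × 10^9/L, the first value that can be graded is 100/11 = 9.1 to 100/10 = 10 times ULN. Any count between ULN and 100 × 10^9/L gets no grade.

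**2. White-cell subtypes.** Eosinophils are graded from "> ULN and > baseline" (Grade 1), and lymphocytes from "> 4000 – 20,000/mm" (Grade 2, per cubic millimetre). Rises in these two subtypes can therefore appear. A neutrophil rise cannot, because there is no row for it.

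**3. Glucose, high.** None of the four grades has a numeric threshold. Grade 1 can be decided from the value, the baseline and the reference range. Grades 2, 3 and 4 cannot be decided from a laboratory value, and Section 9.5.2 has no rule that brings medication or adverse event data into the grade. So the table can show that glucose rose, but not how far.

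**4. Tests without a row.** Protocol Section 10.3.6 lists 22 biochemistry tests, counting eGFR with creatinine. Fourteen have at least one row: sodium, potassium, bicarbonate, glucose, creatinine, creatine kinase, calcium, albumin, total bilirubin, amylase, GGT, ALP, ALT and AST. The other 22 − 14 = 8 have none: chloride, urea, phosphate, troponin-I, lipase, total protein, conjugated bilirubin and hemoglobin A1C.

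**5. What the other outputs give for these tests.**

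| Planned output | What it shows | What it does not show |
|---|---|---|
| By-visit n, mean, median, SD, minimum, maximum, and change from baseline (SAP 9.1, 9.5.2) | The most extreme value in each group at each visit | How many subjects were out of range, whether they are the same ones across visits, and whether they were normal at baseline |
| Peak or lowest post-baseline values (SAP 9.5.2) | ALT, AST, ALP, bilirubin; hemoglobin, platelets | Leukocytes, neutrophils, glucose and the eight tests above |
| Key laboratory plots (SAP 9.5.2) | ALT, AST, total bilirubin, creatine kinase, creatinine, potassium, sodium | The same tests |
| Flagged listings (SAP 9.5.2) | Every out-of-range value, by subject | A count by dose group |
| Adverse event tables (SAP 9.5.1) | Subject counts by group for abnormalities reported as events | Abnormalities that the investigator did not judge clinically significant and that had no sequelae (Protocol 11.2) |

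No row of this table yields an objective count by dose group of subjects who crossed a reference limit.

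**6. Baseline category.** The SAP does not define a Grade 0. A leukocyte count that is raised at baseline but below the Grade 3 cut might be shown as ungraded or as unknown. The table shells are in a companion document that is not available here, so the printed layout cannot be settled.

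**The case against.** The strongest reply is that Appendix A is the CTCAE scale the SAP says it uses, that Section 9.5.2 openly limits grading to selected tests, and that much else is reported. Maxima are tabulated at each visit. Planned active cohorts have only 4 to 18 subjects, so a flagged listing can be read by eye. An abnormality judged clinically significant becomes an adverse event and is counted by group. Protocol Section 12.3 itself provides for listing variables without a code against normal limits. Hemoglobin A1C is in the panel and gets by-visit summaries.

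Most of this stands, and it limits the point to a gap in one type of table. It does not close the gap. Following a grading scale faithfully does not make that scale adequate as the only categorical summary, and the adverse event route depends on clinical judgement.

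Stronger readings are tempting, and the documents do not support them:

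- **That the leukocyte or glucose rows would read zero regardless of effect.** A count above 100,000/mm3 would be Grade 3, an abnormal glucose above baseline would be Grade 1, and the layout of empty rows is unknown.
- **That the SAP plainly breaks a protocol promise.** The synopsis mentions shift tables but does not promise one for each test, and Section 12.3 does not mention them.
- **That lung toxicity would go unseen.** Pulmonary risk is followed by frequent FEV1 with stopping rules, chest X-ray and pulse oximetry, and Cohort 5 adds lavage cell counts and cytokines.
- **That a secondary endpoint is lost.** Change in serum electrolytes is delivered by the by-visit summaries, and potassium and sodium are graded in both directions.

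**Conclusion.** The concern holds in a limited form. The planned shift tables cannot show a total leukocyte rise up to 100,000/mm3, a neutrophil rise, the severity of high glucose, or any shift in eight of the 22 collected biochemistry tests. For these the plan gives group statistics by visit, listings and investigator-judged events. It gives no count by dose group of subjects who left the reference range, which falls short of the protocol's general statement that the incidence of laboratory abnormalities will be summarized.

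Two assumptions apply. The figure of about 9 to 10 times ULN depends on an assumed leukocyte ULN of 10 to 11 × 10^9/L. The glucose statement assumes that grades come from laboratory values alone, since the SAP gives no rule for using other data. The number of subjects affected cannot be estimated from the documents.

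This is a cheap improvement to reporting. It does not call the trial's primary or secondary analyses into question.

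**What to change.** In SAP Section 9.5.2, add a reference-range shift table (low, normal or high at baseline against the highest and, separately, the lowest post-baseline value). Present it by dose and regimen with placebo pooled, as SAP Section 9 already specifies. Include at least leukocytes, neutrophils, glucose and the chemistry tests without an Appendix A row. Build it from the low and high flags already required for the listings.

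Footnote the CTCAE shift tables to say that the leukocyte-increase row gives no grade up to 100,000/mm3, that the glucose-high row cannot go beyond Grade 1 by value, and that neither row is evidence of absence or mildness. State also whether an ungraded baseline value counts as Grade 0 or as unknown.

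The cost is one more table set programmed from existing flags, the matching shells, and a somewhat longer output package. No new data collection is needed.
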